 - cumulative usage of postoperative pain medication- opioid (oxycodone) (at 4 hours, 8 hours, 12 hours, 24 hours, 36 hours, 48 hours postoperatively)
 - Time to first postoperative pain medication
 - Need for additional breakthrough pain medication outside of protocol (amount and type of medication will be documented)
 - Subjective patient pain assessment
 - immediate postoperative pain scale performed in postoperative anesthesia care unit (PACU) and throughout the postoperative period according to current nursing protocol (see above)
 - Patient satisfaction with pain management
 - Time to return of bowel function
 - Time to discharge from the recovery room
 - Time to first ambulation
 - Breastfeeding during hospital stay (assessment of both initiation of and exclusive breastfeeding)
 - Maternal side effects/outcomes
 - Intraoperative: hypotension, nausea, vomiting, pruritus, respiratory depression, prolonged numbness or immobility, failed neuraxial anesthesia requiring intubation, systemic toxicity of local anesthesia
 - Postoperative: fever, postoperative wound separation, postoperative wound infection, skin site irritation, incisional hematoma/seroma formation
 - Other *variables* to be collected:
 - Demographic
 - Maternal: Age, gravidity, parity, number of prior cesarean deliveries, number of prior surgeries, maternal co-morbidities (chronic hypertension, gestational hypertension, preeclampsia, diabetes mellitus -pregestational, gestational-diet or medication controlled- autoimmune disease, known pain syndromes- i.e. fibromyalgia, etc.), reason for current cesarean delivery, history of tobacco use, history of anxiety or depression, amniotic membrane status, body mass index, ethnicity
 - Fetal: gestational age, suspected intrauterine growth restriction, estimated fetal weight, known or suspected congenital or chromosomal anomalies, placenta previa
 - Intraoperative variables

- Length of surgery, estimated blood loss, intraoperative complications, concurrent bilateral tubal ligation, any other analgesia given intraoperatively and amount of other anesthetic given
- Postoperative variables
 - Neonatal outcomes (will be stratified based on fetal gestational age as this study includes all gestational ages and neonatal outcomes will likely be affected by gestational age; we will therefore stratify results by completed weeks of gestation: >37 weeks, 34-37 weeks, 30-34 weeks, <30 weeks)

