 - APGARS, APGAR <7 at 5 min, fetal arterial blood gas pH and base deficit, neonatal intensive care unit admission, fetal weight
- **Study Population:** all pregnant female patients who will be undergoing an elective cesarean delivery under spinal anesthesia at any gestational age
 - Inclusion criteria:
 - Elective cesarean delivery with or without planned bilateral tubal ligation
 - Planned spinal anesthesia
 - Planned Pfannenstiel or low transverse skin incision
 - Exclusion criteria:
 - Known maternal allergy to bupivacaine or derivative
 - Known maternal allergy to oxycodone, ibuprofen, acetaminophen or derivative
 - Currently have an epidural catheter in place
 - Planned general anesthesia
 - Maternal age <18 years old
 - Emergent cesarean delivery
 - Active labor [defined as: >6cm cervical dilation and regular contractions noted on tocometer (>2 contractions in a 10 minute period for 30 consecutive minutes)]
 - Chronic antepartum opioid use
 - History of substance abuse (alcohol or drug)
 - Current tobacco use
 - Chronic steroid use or needing stress dose steroids at the time of delivery
 - Medical contraindication to neuraxial anesthesia such as thrombocytopenia (platelet count <80,000/microliter) or space occupying lesion of the brain
 - Category 3 fetal heart rate pattern

- Maternal fever or suspected chorioamnionitis
 - Concern for morbidly adherent placenta
 - Planned cesarean hysterectomy
- **Power analysis:**
 - Sample size was determined assuming a power of 80%, p value of 0.05 to detect a 25% difference in the primary outcome of cumulative opioid usage in the first 24 hours postoperatively
 - In a previous unpublished, randomized controlled study conducted by [name], average use of opioids in post-cesarean subjects was 47mgSD 35 morphine equivalence in the first 24 hours postoperatively
 - Therefore, in our protocol, with three groups and keeping the hypothesis as one of the groups will consume fewer opioids (SD as 25) to demonstrate a minimum 25% difference between any two groups, this will require 255 subjects total (85 subjects per group). However, to accommodate for missing data and study withdrawal we will increase the sample size by 10 % therefore there will be 276 subjects total- or 92 patients per group
- **Exclusion of any population group:**
 - Minors <18 will be excluded
 - There are regulations for protection of human subjects allowing consenting adults to accept a higher level of risk than is permitted for children

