 - Hypothesis: The addition of incisional subcutaneous bupivacaine with epinephrine to standard spinal anesthesia regimen at the time of elective cesarean delivery will decrease postoperative narcotic usage by at least 25% in the first 24 hours
 - A statement regarding specifically what data are to be used to test the hypothesis (or to generate the hypotheses)
 - Our hypothesis will be tested by assessing cumulative postoperative opioid usage in the first 24 hours postoperatively
 - The statistical method(s) to be used to test the hypothesis with that data
 - Depending on the distribution of the data appropriate statistical analysis including one way ANOVA or non-parametric Kruskal Wallis test will be used to analyze the data. Categorical variables such as adverse events, we will be analyzed using Chi-Square analysis. Additionally, we will be using a linear mixed effects regression analysis to model the difference in mean pain scores during the hospital stay.
 - A power analysis to determine the sample size
 - See above for sample size calculation in Methods section) for power analysis
 - Describe methods for interim analyses or early stopping, if applicable
 - Data Safety Monitoring Board (DSMB) will review interim findings at the midpoint of the study. The study will be terminated early if

evidence of effect is established, if the intervention appears futile, or if harm is established. Specifically, if the p-value of the intervention-by-time effects based on data accumulated by the midpoint of the study is smaller than 0.005 (O'Brien-Fleming boundary), we will declare the superiority of the intervention. On the other hand, if the upper bound of the 95% confidence interval for the difference between the groups is less than 5%, we will declare futility of the intervention. The DSMB will also be authorized to recommend early termination for other reasons related to patient safety. We will have a planned interim analysis halfway through patient recruitment to stop the study if there is a significant impact

- Describe how possible confounding and/or effect modification will be addressed
 - All patients will be randomized and blinded to their intervention groups. Baseline demographic variables will be collected to assess for differences among the groups. Patients with a history of chronic pain syndromes or chronic opioid use will be excluded from the study.
- Describe how loss to follow up will be addressed

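### The primary comparison is unadjusted and no covariates are pre-specified; this is valid, but it may forgo precision and leaves any adjustment to be chosen after the data are seen

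*Combined protocol and SAP*

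**What the plan says.** **Primary test.** The Data Analysis section says that, depending on the distribution, "one way ANOVA or non-parametric Kruskal Wallis test will be used to analyze the data". No covariate is named. The only regression model in the plan is a mixed model for pain scores, a secondary outcome, and it names no covariates either.

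**Baseline data.** Under confounding and effect modification, the same section says: "Baseline demographic variables will be collected to assess for differences among the groups". No step follows from that comparison.

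**What is collected.** The maternal variables in the list of other variables to be collected include "number of prior cesarean deliveries, number of prior surgeries", body mass index and history of anxiety or depression. Tubal ligation appears in two places. The inclusion criteria admit "Elective cesarean delivery with or without planned bilateral tubal ligation", but the only ligation item on the data list is the concurrent procedure, under intraoperative variables.

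**Design.** Randomisation is in blocks of 6 with no stratification factor, so the design does not balance any of these variables. Gestational age stratifies neonatal outcomes only.

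**The concern.** There are two separate issues.

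1. **Pre-specification.** In a randomised trial, differences between arms at baseline arise by chance. Looking for them, with no rule for what happens next, leaves open whether the primary result will be adjusted and for what. A choice made after seeing the data is hard to defend. This issue does not depend on how prognostic the covariates are.
2. **Precision.** If the collected variables predict opioid use, a linear model with arm and covariates estimates the same difference in means as the ANOVA, with residual variance multiplied by about (1 − R-squared). That means narrower intervals and more power from the same patients.

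**Working it through.** **Inputs, all from the Power analysis section.**
- Power and alpha: "Sample size was determined assuming a power of 80%, p value of 0.05".
- Source study: mean opioid use "was 47mgSD 35 morphine equivalence in the first 24 hours postoperatively".
- SD and effect used: "SD as 25) to demonstrate a minimum 25% difference between any two groups".
- Result: "this will require 255 subjects total (85 subjects per group").
- Difference: 0.25 × 47 = 11.75 mg.
- R-squared of the covariates: not in the documents. The values 0.05, 0.10 and 0.20 are assumed.

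**Step 1: reproduce the plan's figure.** Use the omnibus F test for three groups with means at −d/2, 0 and +d/2. The noncentrality is λ = n × (d²/2) / SD², with 2 and 3n − 3 degrees of freedom.
- d rounded to 12 mg, SD 25, n = 85: λ = 85 × 72 / 625 = 9.79 and power is 80.2%. The smallest n reaching 80% is 85 per group, 255 in total, exactly as stated.
- d = 11.75 mg, SD 25: 89 per group are needed. At 85, λ = 85 × 69.03 / 625 = 9.39 and power is 78.4%.

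The stated size therefore fits an unadjusted three-arm ANOVA and does not rely on adjustment.

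**Step 2: add covariates.** Replace SD² by SD² × (1 − R²) and allow 5 degrees of freedom for covariates, so the error degrees of freedom fall from 252 to 247. The approximate half-width of a pairwise 95% CI is 1.96 × SD × √(1 − R²) × √(2/85). All rows use d = 11.75 mg and 85 per group.

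| R² (assumed) | Power, SD 25 | Half-width, SD 25 | n per group for 80%, SD 25 | Power, SD 35 | Half-width, SD 35 |
|---|---|---|---|---|---|
| 0 (unadjusted) | 78.4% | 7.5 mg | 89 | 48.1% | 10.5 mg |
| 0.05 | 80.6% | 7.3 mg | 84 | 50.2% | 10.3 mg |
| 0.10 | 82.8% | 7.1 mg | 80 | 52.5% | 10.0 mg |
| 0.20 | 87.1% | 6.7 mg | 71 | 57.8% | 9.4 mg |

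**Step 3: the price if the covariates predict nothing.** With R² = 0 and 5 degrees of freedom spent, λ stays at 9.39 and power at SD 25 is still 78.4% to one decimal.

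**Step 4: sensitivity to the middle arm.** Omnibus power depends on where the third mean lies. If two arms are equal and one differs by 11.75 mg, unadjusted power is 89.3% (SD 25) or 60.7% (SD 35). A single two-sample t-test at two-sided 0.05 gives 86.1% or 58.6%, but that is not the test the plan names.

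**Step 5: can adjustment bridge the two SDs?** To bring a residual SD of 35 down to 25, R² would have to be 1 − 625/1225 = 0.49, well beyond the range assumed here.

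**The case against.** The strongest case for the plan is that nothing here is wrong. An unadjusted test is valid after randomisation, the sample size was built for it, and no two sections conflict on this point. That stands, and it makes this an improvement, not a correction.

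The benefit is also assumed. No section says that these variables predict opioid use, and the exclusions for chronic opioid use, substance abuse and current tobacco use may leave less variation to explain. A reader might infer that the plan is certain to lose precision. The documents do not support that: at R² = 0.05 the gain is about 2 percentage points, and it may be nil.

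A reader might also infer that the plan intends significance tests of baseline differences, with adjustment triggered by the result. It says neither, and a purely descriptive table fits its wording. What stands is that the plan does not rule such adjustment out.

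Two technical objections hold and shape the fix. Kruskal-Wallis does not target a difference in means, and with mean 47 and SD 35 for an outcome that cannot be negative, skew is likely. A proposed model must therefore allow for skew. And tubal ligation cannot simply be added as a baseline covariate, because the listed variable is the procedure performed at surgery.

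**Conclusion.** The point holds as an inexpensive improvement. The primary comparison is valid but unadjusted, and the plan fixes no adjustment in advance.

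The possible gain at 85 per group is about 2 to 9 percentage points of power at SD 25 (78.4% to between 80.6% and 87.1%) and about 2 to 10 at SD 35 (48.1% to between 50.2% and 57.8%). This rests on an assumed R² of 0.05 to 0.20, evenly spaced arm means, a true difference of 11.75 mg and the omnibus F test. The case for pre-specification needs none of these assumptions.

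It would be tempting to present adjustment as the remedy for low power. It is not. The gap between the SD of 25 used and the SD of 35 cited is a separate matter that must be resolved in its own right. Adjustment also deals only with chance imbalance in the covariates included, as they are modelled.

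**What to change.** Before unblinding, amend the Data Analysis section as follows.

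- Make the primary analysis a linear model for 24-hour morphine equivalents with arm and four covariates: number of prior cesareans, number of prior surgeries, body mass index, and history of anxiety or depression. State how each enters the model and how missing covariate values are handled.
- Use robust standard errors, so that the difference in means stays the target if opioid use is skewed. Report adjusted arm differences with 95% CIs.
- Keep the unadjusted ANOVA or Kruskal-Wallis test as a sensitivity analysis.
- State that the baseline table is descriptive and does not determine the covariates.
- Add tubal ligation only if the plan for it is recorded before randomisation. Do not use the intraoperative concurrent-ligation variable.
- Leave known pain syndromes out of the model until the documents are reconciled. The Data Analysis section says chronic pain syndromes are excluded, the exclusion criteria do not list them, and the variable list collects them.

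The cost is SAP wording and about 5 of 252 error degrees of freedom. The four covariates need no new data; recording planned ligation would be a new item.
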